### **9.3.2.3. Preterm birth**

An infant born at gestational age <37 weeks

### **9.3.2.4. Small for gestational age (SGA)**

Birthweight  $\leq$ 10th percentile for gender and gestational age using the NCHS pediatric growth curves for full term infants. Prenatal growth curves will be used for preterm infants.

### **9.3.2.5. Maternal pregnancy complications**

Pre-eclampsia, hypertension in pregnancy

**9.3.2.6. Infant outcomes**

Gestational age, birth weight, sex

**9.3.2.7. Infant events of interest**

Dates of follow-up evaluation, current age of infant, weight, developmental milestones per the infant's HCP's assessment of normal, delayed, etc.

**9.3.3. Other Variables**

Other variables will be collected for the description of baseline characteristics of the study population or to determine gestational age or the presence of possible confounding factors.

**9.3.3.1. Maternal characteristics**

Age, ethnicity, race, occupation, BMI

**9.3.3.2. Paternal characteristics**

Age

**9.3.3.3. Prenatal data**

Last menstrual period (LMP), estimated date of delivery (EDD), corrected estimated date of delivery (CEDD), singleton or multiple pregnancy

**9.3.3.4. Prenatal tests**

Name of test, date of test, result

**9.3.3.5. Obstetrical history**

Previous pregnancies (singleton/multiple) and their outcomes (live births, stillbirths, SABs, elective terminations), births with congenital malformations, family history of congenital malformations

**9.3.3.6. Co-morbid medical conditions**

Diabetes, hypertension, depression

**9.3.3.7. Concomitant medications and vaccines**

Prescriptions and over-the-counter medications including fertility treatment and migraine treatment

**9.3.3.8. Substance use**

Alcohol, tobacco, and illicit drug use

**9.4. Data Sources**

The pregnant woman and appropriate members of her and her infant's health care team will serve as data reporters to the study. The study is strictly observational; patient care and treatment regimens will be determined by the treating HCP. There will be no additional laboratory tests or assessments required as part of this study. Any additional tests during pregnancy will only be done on the basis of the pregnancy needs and as decided on by the treating HCP. Only data recorded as part of routine care will be collected. The following table

provides a summary of data that will be collected at specific time points and the source of data.  
[Further details on the operational definitions are provided under 9.4.1, 9.4.2 and 9.4.3.]

**Table 1. Summary of patient follow-up and data collection timepoints**

Information Requested	Maternal Contact (Patient)		Maternal HCP Contact			Infant HCP Contact		Evaluator
	Enrollment	Outcome e	Registration	Interim Follow-Up (2 nd trimester)	Outcome Follow-Up	Follow-Up (at birth) f	Follow-Up (4 and 12 months)	Targeted Follow-Up
Reporter Information and Permissions								
Report source, permission to contact HCP (for pregnant patient), pediatrician, and alternate patient contact information as applicable	✓	✓ e	✓					
Maternal Information								
Maternal characteristics (age, ethnicity, disease status)	✓		✓					
Maternal prenatal information (LMP, EDD, CEDD, prenatal test results & timing)	✓		✓	✓ a	✓ a			
Obstetrical history (maternal and paternal)	✓		✓					✓ d
Family history (maternal and paternal)	✓		✓					
Galcanezumab therapy (indication for use, dates of administration) (maternal/paternal as appropriate)	✓ g		✓	✓ a, g	✓ a, g			
Concomitant medications (Rx, OTC, dietary supplements, herbals), during pregnancy (dosage, routes, start/stop date of administration), recreational/illicit drug, alcohol and tobacco use during pregnancy	✓		✓	✓ a	✓ a			
Maternal concurrent medical conditions	✓		✓	✓ a	✓ a			

Outcome of Pregnancy Information								
Pregnancy status	✓		✓	✓	✓ a			
Outcome information (fetal loss, live birth, gestational age, weight)				✓ b	✓	✓ f		
Birth defect noted, description, attribution, if applicable				✓ b	✓			
Other factors that may have contributed to outcome (etiology)				✓ b	✓			✓ d
Infant Follow-up Information								
Birth defect noted, description, attribution, if applicable						✓ cf	✓ ac	
Other factors that may have contributed to outcome (etiology)						✓ cf	✓ ac	✓ d
Developmental delays noted						✓ f	✓ ac	

a Obtain updated information since the previous contact.

b Obtain this information if outcome has occurred.

c Collect only for live birth outcomes.

d Collect information not previously obtained, to facilitate the characterization of the fetal loss and/or birth defect(s).

e Contact to obtain Medical Information Release Form for Pediatrician if not previously obtained.

f Collect only if unable to collect at birth from Maternal HCP contact.

g Applicable for galcanezumab exposed group only.

### **9.4.1. Overview of data collection process**

#### **9.4.1.1. Information Collected at Enrollment**

After applicable patient informed consent is obtained from the eligible woman, the reporter will complete the *Registration Form* and submit it to the RCC.

##### *Maternal and Paternal Information*

- Maternal and paternal demographics
- LMP
- EDD determined from LMP
- CEDD (e.g. by ultrasound) if available
- Singleton or multiple pregnancy
- Prenatal tests (diagnostic or screening) performed, date of test(s), and findings including the identification of congenital anomalies

##### *Maternal Obstetrical History*

- Number of previous pregnancies (singleton or multiple)
- Outcome of all previous pregnancies
- History of offspring with congenital anomalies
- Maternal and paternal history of congenital anomalies

*Maternal Galcanezumab Exposure* (in case of self-enrollment of a galcanezumab exposed pregnancy, to be provided initially by the pregnant woman at study enrollment and confirmed by the treating HCP)

- Galcanezumab injection(s), including date(s) and indication for use

##### *Other Conditions and Exposures*

- Concurrent maternal conditions, including migraine
- Concomitant medications taken during pregnancy, including fertility treatments and migraine treatments

- Tobacco, alcohol, and illicit drug use during pregnancy

#### **9.4.1.2. Information Collected at Pregnancy Follow-up**

Around the end of the second trimester and in the month of the EDD, the *Interim Pregnancy Follow-up Form* and *Pregnancy Outcome Form* (respectively) will be requested from the obstetric HCP or the patient, if applicable. For subjects that enroll late in pregnancy, the End of Second Trimester follow-up might not be applicable. In the month of the expected date of delivery, the Registry prompts the pregnant patient's HCP to complete the *Pregnancy Outcome Form*. The patient is also contacted to provide authorization for medical release for the baby's pediatrician (if not previously obtained).

##### Follow-up at End of Second Trimester

###### *Pregnancy Status*

- Updates to expected date of delivery (i.e., CEDD)
- Subsequent prenatal tests (diagnostic or screening) performed and findings including the identification of congenital anomalies
- Pregnancy complications (preeclampsia, hypertension during pregnancy)
- Details of pregnancy outcome if pregnancy is no longer ongoing (see Follow-up at Pregnancy Outcome)

###### *Other Exposures during pregnancy*

- Concomitant medications (including migraine medications)
- Tobacco, alcohol, and illicit drug use during pregnancy

##### Follow-up at Pregnancy Outcome

###### *Pregnancy Outcome*

- Pregnancy outcome (live birth, stillbirth, SAB, elective termination, ectopic, molar)
- Date of outcome of pregnancy
- Gestational age at outcome
- Fetal/infant characteristics: gender, birth weight
- Congenital malformation(s) and potential contributing factors
- For a fetal loss (SAB, stillbirth), factors that may have had an impact on the fetal loss

#### **9.4.1.3. Information Collected at Pediatric Follow-up**

##### *Timing of Pediatric Follow-Up*

If a live birth occurs, the mother is asked to give consent for the infant's pediatrician to provide follow-up information. If consent is obtained, the pediatrician completes the *Pediatric Follow-Up Form* at 4 and 12 months of age.

Pediatric Follow-up FormInfant Outcome

- Date of follow-up evaluation
- Current age of infant
- Current weight of infant
- Developmental milestones per the HCP's assessment of normal, delayed, etc.
- Congenital malformation(s) and details, if noted
- Type of congenital malformation(s) if applicable, attribution to galcanezumab drug therapy, and other factors that might have contributed to the outcome

Targeted Follow-up after report if an event of interest

If there is a congenital malformation, in order to properly characterize the event, additional information may be requested from the reporting HCP on the *Targeted Follow-up Form*:

- Details of the congenital malformation
- Etiology
- Maternal infections of relevance to congenital malformations
- Other information considered relevant by the HCP
- Specific questions requested by the congenital malformation evaluator

**9.4.2. Follow-up process**Attempts to Obtain the Follow-Up Information

In the month that the follow-up is due, the HCP will be contacted and asked to provide follow-up information. Three subsequent attempts, as necessary, will be made every two weeks via various modes of communication, e.g., phone, fax, email, mail. If the missing follow-up data is essential to characterize the outcome or event and there is still no response from the provider, a final communication will be sent indicating the case is lost to follow-up. If this communication prompts a response from the HCP or the requested data is later received, the case will be re-opened and assessed for evaluability. If, at any point in the follow-up process, the reporter specifically indicates that the patient is lost to follow-up, no further attempts will be made, but an attempt to obtain information on the cause of loss to follow-up will be made.

Follow-Up Process for Clarification of Information

For critical data points, if there are outstanding questions, discrepancies between forms, or missing data, the appropriate reporter will be contacted for clarification. Three subsequent attempts, as necessary, will be made every two weeks. If no further information is obtained on an otherwise evaluable case, the discrepant information in the data fields may be left blank or identified as “unspecified” or “missing”. On a case-by-case basis, qualified study staff may make

a determination on discrepant information (e.g., determination of partially illegible word or illogical year) in accordance with electronic Case Report Form Completion Guidelines (eCRGs).

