#### **9.2.4.2. External Comparator Data**

The use of external comparators will be considered as supplemental, exploratory comparison groups to contextualize the findings of the registry. The published final results of the Sumatriptan, Naratriptan, Treximet Pregnancy Registry (Ephross and Sinclair 2014) represent a readily available external non-CGRP antagonist exposed historical pregnant migraine population. However, it is important to note that only major birth defects apparent at birth were captured, as infants were not followed up to one year of age. In addition, while some pregnancy outcomes including spontaneous abortions, fetal death/stillbirths and elective terminations were collected, other outcomes of interest such as pre-eclampsia, hypertension during pregnancy, preterm birth, small for gestational age, and postnatal growth/ development through one year of age were not collected.

Published results from the Metropolitan Atlanta Congenital Birth Defects Program (MACDP) for congenital malformations, as well as published data for other outcomes of interest (e.g. the CDC National Vital Statistics System (NVSS) for the US prevalence of preterm birth (Martin et al. 2015) can serve as a secondary supplemental background comparator with the internally enrolled comparison group as the primary comparator. While the MACDP is considered to be the standard coding criteria for congenital malformation evaluation, there are well known limitations such as geographic representation and patient demographics that are not ideally reflective of the whole US population. External comparators are still useful to allow the assessment of generalizability of this study’s findings and any other future study findings.

Should other newly available or newly identified appropriate supplemental migraine and/or population-based comparison data from the literature and other sources, such as other pregnancy registries or observational studies become available, these will be evaluated as possible additional data to contextualize further the results of this study.

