### **9.3.2.2. Congenital Malformations**

The study defines and codes congenital malformations with criteria specified by CDC MACDP (CDC 2007). A major congenital malformation (MCM) is defined as any major structural or chromosomal defect in live-born infants, stillbirths, or fetal losses of any gestational age (including outcomes prior to 20 weeks' gestation or birth weight <500 g). This definition is consistent with, but not restricted to, the CDC MACDP definition. Clusters of conditional abnormalities (i.e., minor congenital malformations as defined by CDC MACDP) and data from aborted fetuses of less than 20 weeks' gestation, when available, will be included to increase sensitivity of monitoring. The MACDP includes conditional defects only if in the presence of a major defect. This study will consider reports of three or more conditional defects as a defect case, to increase case detection sensitivity and to capture instances where a combination of conditional events might constitute a major defect or syndrome.

The study conforms to the CDC MACDP guidelines; it disqualifies as defects those findings that are present in infants born at less than 36 weeks of gestation and which are attributable to prematurity itself (such as patent ductus arteriosus, patent foramen ovale, or inguinal hernias). The CDC MACDP classification does include chromosomal defects. Though these defects are not likely to contribute to a risk for a medication exposure, the study includes these defects to maintain this consistency with the CDC MACDP.

Live-born infants with only transient or infectious conditions or with biochemical abnormalities will be classified as being without reported congenital malformations unless there is a possibility that the condition reflects an unrecognized defect. Detected and reported transient or infectious conditions or biochemical abnormalities in infants without reported MCMs and defects that are excluded by the CDC guidelines will be noted in an appendix in the study reports.

The Registry will systematically collect information on major structural and chromosomal defects that are apparent at birth and noted through infant age one year: congenital malformation(s) and details, if noted, type of congenital malformation(s) if applicable, attribution to drug therapy, and other factors that might have contributed to the outcome.

If a congenital malformation is reported, other data of interest can be collected through targeted follow-up.

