## 9.5. Study Size

The study aims to enroll a minimum of 420 prospectively enrolled evaluable pregnant women with galcanezumab exposure. Approximately 420 galcanezumab exposed pregnancies are needed to have 80% power to detect a 2.0 fold difference in the baseline risk of major malformations (2.78%) relative to women in the general population.

Assuming 10% loss to follow-up, it is anticipated that approximately 470 patients need to be enrolled. Research indicates that approximately 83% to 95% of pregnancies enrolled in pregnancy exposure registries result in a live birth (Covington et al. 2010), resulting in a lower estimate of approximately 350 and an upper estimate of 400 live births.

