### **9.7.2. Statistical Methods**

Overall and stratum-specific (e.g., timing of exposure to galcanezumab (prior to conception vs. during pregnancy, as well as trimester of exposure), maternal age group) point estimates and 2-sided 95% confidence intervals will be calculated using the exact binomial distribution for prevalence of congenital malformations among evaluable patients, preterm birth and SGA among evaluable patients with live births, preeclampsia and hypertension in pregnancy and infant growth and development through one year for each of the galcanezumab exposed, CGRP antagonist-unexposed migraine and general population, non-migraine groups.

If applicable, frequencies of the events of interest will be presented by pregnancy outcome.

Most structural defects have their origins in the first trimester of pregnancy, the period of organogenesis. In addition to overall prevalence of observed MCM, the analysis of MCMs will be stratified by trimester of earliest exposure to galcanezumab. The prevalence of combined MCMs reported to the study will be calculated as a proportion with the number of observed MCMs as the numerator and the number of live births as the denominator, among women with first trimester exposure. CDC MACDP uses these figures to calculate the prevalence, and in order to compare the observed study prevalence with the background prevalence, it is decided to use the same method. Pregnancy losses occurring at or after 20 weeks' gestation with reported MCMs will be included in the numerator of the estimate of prevalence for MCMs as a conservative approach. This method also allows comparison of outcomes with the CDC MACDP. The reason MACDP uses this method is because a slight overestimate is preferred to a potential underestimate. This is due to not taking into account stillbirths in the denominator (but counting the MCM's recognized in stillbirths in the numerator). However, given the very low prevalence of stillbirths as pregnancy outcomes in the general population, this is only a very small possible overestimate. The prevalence of observed MCMs in exposed cases will be compared with the most recent reported prevalence of the CDC MACDP. Additionally, if a sufficient sample size is attained for each trimester exposure group, it may be possible to compare the prevalence of MCMs among exposures to galcanezumab in the first trimester versus

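### Malformations are counted through one year, but live births with no report after birth stay in the denominator as unaffected by later-noted defects, so the one-year prevalence is biased downward

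*Protocol*

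**What the plan says.** **Case window.** The protocol abstract (section 4) lists congenital malformations up to one year of age as the main outcome. Section 9.3.2.2 collects major defects "that are apparent at birth and noted through infant age one year".

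**How later defects are found.** The maternal health care provider (HCP) reports malformations at the pregnancy outcome (9.4.1.2, 9.4.4). After that the source is the pediatric form at 4 and 12 months. Under 9.4.1.3 the mother is asked for consent after a live birth, and "If consent is obtained, the pediatrician completes the" form.

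**Prevalence rule.** Section 9.7.2 takes the "number of observed MCMs as the numerator and the number of live births as the denominator", for women with first-trimester exposure. Losses at 20 weeks or later with an MCM are added to the numerator. The section defends this by saying that it would rather err slightly high than low.

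**Who stays in.** A woman is evaluable once the pregnancy outcome and the presence or absence of a malformation are known (section 4, 9.2.3.1); no age at assessment is given. Section 9.9 defines loss to follow-up by a missing pregnancy outcome only. Section 9.6 keeps incomplete cases with their data to last collection. Cumulative data are analysed and reported every year (9.2.1, 9.7).

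**External data.** Section 9.2.4.2 notes that in the triptan registry "only major birth defects apparent at birth were captured, as infants were not followed up to one year of age".

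**The concern.** The numerator can gain cases for a year after birth, but only from infants whose pediatrician reports. The denominator makes no such demand. An infant with a clean birth report and no pediatric form is treated as observed to be free of malformation for 12 months, when that is unknown for anything not visible at birth.

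Section 9.9 recognises this problem for fetal losses. It leaves out losses without a diagnosed MCM because their status is uncertain and counting them could misclassify. There is no matching rule for live births whose status after birth is uncertain.

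At stake is the main outcome. The bias runs towards reassurance, which is the direction 9.7.2 says it wants to avoid. In annual reports it does not depend on non-response: any live birth less than 12 months old at the cutoff is in the denominator with an incomplete window. If pediatric reporting differs between cohorts, the relative comparison in the secondary objective is distorted too. The routes into the cohorts differ (9.2.4.1 allows self-referred migraine controls and friend referrals for the non-migraine group), so unequal follow-up is possible, though the protocol does not say that it is expected.

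**Working it through.** **1. The plan's own size figures (9.5).** Stated: "Approximately 420 galcanezumab exposed pregnancies are needed" for "80% power to detect a 2.0 fold difference in the baseline risk of major malformations (2.78%) relative to women in the general population". Alpha is not stated; I assume two-sided 0.05.

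One-sample normal approximation against a fixed p0 = 0.0278, with p1 = 0.0556:

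n = [1.96·√(p0(1−p0)) + 0.842·√(p1(1−p1))]² / (p1−p0)² = 344 live births.

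344 / 0.83 = 415 pregnancies, close to 420. Next, "Assuming 10% loss to follow-up, it is anticipated that approximately 470 patients need to be enrolled": 420 / 0.90 = 467. Last, "resulting in a lower estimate of approximately 350 and an upper estimate of 400 live births": 420 × 0.83 = 349 and 420 × 0.95 = 399. All three figures reproduce. The 10% loss applies to enrolled patients and makes no separate allowance for missing pediatric forms.

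**2. Bias in prevalence.** Let p be the true 12-month MCM prevalence, L the share of MCMs first noted after the birth report, and m the share of live births with no pediatric follow-up. Take m as unrelated to malformation status, and treat follow-up as all or nothing. Cases seen at birth, p(1−L), are all counted; later cases, pL, are counted only in the fraction 1−m. So

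observed / true = (1−L) + L(1−m) = 1 − L·m.

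The protocol gives neither L nor m, so both are assumptions. Power below is for 349 live births against a fixed 2.78%, with the observed prevalence p1·(1 − L·m) in place of p1:

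Power = Φ{[(p1−p0)√n − 1.96√(p0(1−p0))] / √(p1(1−p1))}.

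| L | m | 1 − L·m | true 2.78% seen as | true 5.56% seen as | ratio to 2.78% | power |
|---|---|---|---|---|---|---|
| none | none | 1.00 | 2.78% | 5.56% | 2.00 | 80.5% |
| 10% | 10% | 0.99 | 2.75% | 5.50% | 1.98 | 79% |
| 20% | 10% | 0.98 | 2.72% | 5.45% | 1.96 | 78% |
| 40% | 10% | 0.96 | 2.67% | 5.34% | 1.92 | 76% |
| 30% | 20% | 0.94 | 2.61% | 5.23% | 1.88 | 73% |
| 20% | 40% | 0.92 | 2.56% | 5.12% | 1.84 | 70% |
| 40% | 40% | 0.84 | 2.34% | 4.67% | 1.68 | 56% |

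**3. Bias between cohorts.** Observed ratio / true ratio = (1 − L·m_exposed) / (1 − L·m_control). With equal m this is 1. At L = 30%:
- 30% missing in exposed and 10% in controls: 0.91 / 0.97 = 0.94, so a true 2.0 is seen as 1.88.
- 10% missing in exposed and 30% in controls: 0.97 / 0.91 = 1.07, so a true 2.0 is seen as 2.13.

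**4. Does censoring repair it?** Take p = 2.78% and L = 30%. At birth, 0.70 × 2.78% = 1.946% is seen in all live births. Among followed infants the later risk is 0.834% / 98.054% = 0.851%. Cumulative incidence = 1 − (1 − 0.01946)(1 − 0.00851) = 2.78%, whatever m is, provided that missing forms are unrelated to malformation.

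**5. A repair that fails.** Restrict the denominator to infants with a 12-month form plus every MCM already found. With L = 30% and 60% followed:
- Cases: 0.88 × 2.78% = 2.446%.
- Non-cases with a form: 0.6 × 97.22% = 58.33%.
- Prevalence: 2.446 / 60.78 = 4.03% for a true 2.78%.

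With 80% of exposed and 50% of controls followed, a true ratio of 1.0 becomes 3.25% / 4.64% = 0.70. Cases are kept regardless of follow-up while non-cases are dropped, so this is worse than the present rule.

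**The case against.** Several points on the other side stand.

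- A reader might infer that an infant without a pediatric form counts as free of any malformation. That is too strong: the maternal HCP reports defects at outcome, and those remain cases. Only later-noted defects are at risk.
- The live-birth rule is written for women with first-trimester exposure and chosen to match the Metropolitan Atlanta program. Another sentence of 9.7.2, covering all three cohorts, refers to evaluable patients. Section 9.4.2 can close a non-responding case as lost when the missing data are essential. But evaluability needs no pediatric form, and 9.4.2 does not say that an infant with a birth report leaves the denominator, so neither removes the problem. Matching an external convention justifies using live births; it does not turn unobserved months into observed ones.
- Permission to contact the infant's HCPs is an inclusion criterion (9.2.2), and each form is chased three further times (9.4.2). This may keep m low. It does not secure a reply, and 9.4.1.3 still makes the form conditional on consent.
- A reader might infer that late enrollees cannot reach 12 months before 30 November 2032. The protocol does not support this: that is the end of data collection, no last enrollment date is given, and 9.2.1 plans follow-up at 4 and 12 months for live births.
- The triptan registry's birth-only window is disclosed, external data are labelled exploratory, and an at-birth count can be derived from the data collected. Not naming that table is no error in itself.

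**Conclusion.** The point holds in limited form. The protocol itself fixes a one-year case window over a live-birth denominator, and nothing removes or censors infants without a report after birth. The one-year MCM prevalence is therefore biased downward, in annual reports also through infants not yet 12 months old.

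The size rests on assumed L and m: 0.96-0.98 of the true value at L = 20-40% and m = 10%, and 0.84-0.92 at L = 20-40% and m = 40%. It is negligible if either is small. No figure in 9.5 becomes wrong, although power against the fixed 2.78% reference falls as L·m grows.

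It would be tempting to conclude that the comparison between cohorts is biased. The documents do not show that: the ratio is unaffected when follow-up is equal, and can move either way when it is not. The change is worth making because the error falls on the main outcome, runs against the protocol's stated preference, and is cheap to remove.

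**What to change.** In 9.7.2, define two MCM figures for each cohort, with its denominator stated:

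- **(a) At birth or pregnancy outcome:** MCMs reported by then over live births, keeping the present treatment of losses at 20 weeks or later. This figure also matches the birth-only triptan registry in 9.2.4.2.
- **(b) Through 12 months:** cumulative incidence of MCM, with infants censored at last pediatric contact (at birth if there is none). Use this for the one-year objective. Show 4- and 12-month form completion by cohort beside it.

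Do not use 12-month completers plus earlier MCM cases as the denominator; it overstates prevalence, as step 5 of the working shows. Say that (b) assumes missing pediatric forms to be unrelated to malformation.

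The cost is one extra derived variable and one table, and a less precise 12-month estimate. No new data are needed.
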